4.5.1 Primary Safety Endpoint

No primary safety endpoint has been defined.

4.5.2 Secondary Safety Endpoints

The secondary safety endpoint is defined in Section 2.2.2.2. Frequency tables for subjects with treatment-related TEAEs and number of treatment-related TEAEs will be provided.

4.5.3 Other Safety Endpoints

- Exposure to study treatment will be analyzed as follows for both treatment periods:
 - For injected volume, descriptive statistics for metric variables will be provided for by injected muscle, muscle group (total injected volume for forearm/wrist muscles, elbow muscles, shoulder muscles), and total injected UL. The number of subjects injected in respective muscle / in at least one muscle of respective muscle group (M) will be displayed as well.
 - For Cycle 1, the analysis will be performed for the injected UL, irrespective of whether the motor dominant UL (acc. to CSP) or the non-dominant UL was treated.
 - For Cycle 2, the analysis will be performed separately by motor dominant and non-dominant UL, and in total for both injected ULs, but only for muscle group and total UL (i.e., total injected volume over both ULs will not be provided separately by muscle). In case, deviating from CSP, not all subjects were treated in both ULs, the analyses will be performed on the subset of subjects treated at the respective UL / both UL(s), as applicable, in Cycle 2. and an explanation (including Subject ID, treatment group, untreated UL [motor dominant or non-dominant] of affected subjects) will be provided in a footnote.

For both cycles, only data with injected volume larger than 0 ml will be included.

- Number of injection points by muscle [including 0 to account for non-injected muscles for treated UL(s)], by muscle, muscle group (sum of injection points over forearm/wrist muscles / elbow muscles / shoulder muscles) and for total injected UL (total sum of injection points of injected UL).
 - For Cycle 1, the analysis will be performed for the injected UL, irrespective of whether the motor dominant UL (acc. to CSP) or the non-dominant UL was treated.
 - For Cycle 2, the analysis will be performed separately by motor dominant and non-dominant UL. In case, deviating from CSP, not all subjects in SES-BP were treated at both ULs, the analyses will be performed on the subset of subjects treated at the respective UL and an explanation (including Subject ID, treatment group, untreated UL [motor dominant or non-dominant] of affected subjects) will be provided in a footnote.
- Adverse events
 - The following summary tables for Section 14.3 of the CSR will be created for total observation period, Cycle 1 and Cycle 2 (if not stated otherwise below):
 - Overall summary of TEAEs, displaying incidences of TEAEs (in total / related to treatment), TEAEs (in total / related to treatment), serious TEAEs (in total / related

- to treatment, TEAEs leading to premature study discontinuation (in total / related to treatment), fatal TEAE (in total / related to treatment) and TEAEs related to COVID-19
- TEAEs, subjects with TEAEs and number of TEAEs by MedDRA SOC and PT
 - TEAEs, subjects with TEAEs by PT
 - TEAEs by worst intensity, subjects with TEAEs
 - TEAEs by worst causal relationship, subjects with TEAEs
 - TEAEs by worst outcome, subjects with TEAEs
 - Serious TEAEs, subjects with serious TEAEs and number of serious TEAEs by SOC and PT
 - Non-serious TEAEs, subjects with non-serious TEAEs and number of non-serious TEAEs by SOC and PT
 - Treatment-related non-serious TEAEs
 - TEAESIs, subjects with TEAESIs and number of TEAESIs by SOC and PT
 - Treatment-related TEAESIs
 - The following by-subject listings of TEAEs occurring in the total observation period will be generated for Section 14.3 of the CSR and include information on treatment cycle:
 - Serious TEAEs, listing of subjects
 - Deaths, listing of all serious TEAEs leading to death
 - TEAEs leading to premature study discontinuation of study, listing of subjects
 - TEAEs of special interest, listing of subjects
 - TEAEs related to COVID-19, listing of subjects.
 - In addition, a complete listing of all AEs (TEAEs and non-TEAEs) occurring in the total observation period will be provided for CSR Section 16.2, also including information on treatment cycle for TEAEs.
- HHD maximum grip strength: Descriptive statistics for HHD maximum grip strength [Newton] (values and changes from applicable cycle baseline, i.e., study baseline for Cycle 1, Cycle 2 baseline for Cycle 2) will be provided by visit for both injection cycles.
 - For Cycle 1, the above-specified analyses will be performed only for treated UL, irrespective of whether the motor dominant UL (acc. to CSP) or the non-dominant UL was treated. Data for non-injected UL will be listed. Furthermore, the intra-individual difference of changes in maximum grip strength from study baseline between hand of treated and hand of untreated UL will be analyzed. The difference will be derived as change from study baseline at hand of injected UL – change from study baseline at hand of non-injected UL.
 - For Cycle 2, maximum grip strength will be summarized separately for motor dominant and non-dominant UL. In case, deviation from CSP, not all subjects in the SES-BP were treated at both ULs, the analyses will be performed on the subset of subjects treated at the respective UL in Cycle 2 and an explanation (including Subject ID, treatment group, untreated UL [motor dominant or non-dominant] of affected subjects) will be provided in a footnote. In case either or both UL are erroneously not injected in Cycle 2, respective values and changes will only be listed.

- [REDACTED]
- [REDACTED]
- [REDACTED]
- [REDACTED]
- [REDACTED]

- Global assessment of tolerability as assessed at Week 24 of unilateral treatment period will be summarized descriptively by treatment group. Week 12 of bilateral treatment period will be summarized descriptively by treatment group and overall. This includes frequency tables and descriptive statistics for metric variables.
- Time course of vital signs (blood pressure, pulse rate), body weight measurement and BMI at selected visits (values and changes from study baseline in both injection cycles) will be summarized descriptively;
- Time course of standard clinical chemistry and hematology parameters measurements at selected visits (values and changes from study baseline in both injection cycles) will be summarized descriptively.

Laboratory values from Screening Visit V1 will serve as study baseline. In case laboratory testing scheduled for Screening Visit V1 was performed after V1 but before Baseline Visit V2 (treatment visit), these values will be analyzed as study baseline. I.e., in line with definition of study baseline provided at beginning of Section 4, baseline flag is 'yes' for last record with non-missing value before first treatment in SDTM). The first valid value is analyzed for a post baseline visit. In addition to descriptive statistics, shift tables from study baseline to Week 24 (V8) and from study baseline to EOS (V11) will be provided.

In case no exact value is given because a laboratory value is below limit of detection and thus provided as <x.x, the respective value (x.x) will be used for calculation of descriptive statistics for metric variables, and <x.x will be listed and flagged accordingly.

- Other safety data will be listed only.

For definition of study baseline and Cycle 2 baseline see beginning of Section 4.

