Since the first observation of possible efficacy of *BoNT A* in the indication of ET [Jankovic 1991], little research has been conducted into this topic. A 2011 update of the American Academy of Neurology treatment guidelines for ET reported that, in the interval since the previous guidelines, new studies providing evidence above Class IV on the efficacy or safety of *BoNT A* for the treatment of ET had not been conducted [Zesiewicz 2011]. Consequently, the guidelines continued their assessment of *BoNT A* as a 'Level C, possibly effective' treatment for ET. The same conclusion was reached in another review [Deuschl 2011], which identified only two double-blind placebo-controlled parallel-design studies of *BoNT A* for the treatment of people with essential hand tremor: the afore mentioned Jankovic study [Jankovic 1996] comparing 50 U (plus an optional booster injection of 50 U after 4 weeks) of onabotulinumtoxinA with placebo, and another larger similarly designed confirmatory study [Brin 2001] in which subjects were randomized to either low-dose (50 U) or high-dose (100 U) onabotulinumtoxinA or placebo. Only the wrist flexors and extensors were injected in both these studies, with flexors receiving 60% of the dose and extensors 40%, and patients were followed up for 16 weeks.

In the second trial, the effect of treatment was assessed by clinical rating scales, measures of motor tasks and functional disability, and global assessment of treatment. Hand strength was evaluated by clinical rating and by a dynamometer. While both doses of botulinum toxin type A significantly reduced postural tremor on the clinical rating scales after 4, 6,

12 and 16 weeks, kinetic tremor was significantly reduced only at the 6-week examination. Measures of motor tasks and functional disability were not consistently improved with botulinum toxin type A treatment. Grip strength was reduced for the low- and high-dose botulinum toxin type A groups as compared with the placebo group. Adverse reactions consisted mainly of dose-dependent hand weakness. The authors concluded that *BoNT A* injections for ET of the hands resulted in significant improvement of postural, but not kinetic, hand tremors and resulted in limited functional efficacy. Hand weakness was found to be a dose-dependent significant side effect of treatment at the doses used in this study [Brin 2001]. The ET therapeutic indication development was consequently not further pursued by the sponsor company.

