5 STUDY OBJECTIVES

The primary objective of this study is to assess the efficacy of unilateral intramuscular injections of NT 201, as compared with placebo, in subjects with ET of the UL.

Secondary objectives are the following:

Safety of unilateral intramuscular injections of NT 201, as compared with placebo, in subjects with ET of the UL.

Efficacy and safety of bilateral intramuscular injections of NT 201 in subjects with ET of the UL.

Redacted version 26Mar2026

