Timepoint		Day 1	WEEK 4	WEEK 6	WEEK 8	WEEK 12	WEEK 18	WEEK 24
Study day	-21 to -3	1	28	42	56	84	126	168
Visit window (days)	19		±3	±3	±3	±7	±7	±7
Visit no.	V1	V2	V3	V4	V5	V6	V7	V8
Informed consent	X							
In- & exclusion criteria	X	X						
Demographics	X							
Medical history/ concomitant diseases	X							
Tremor history	X							
Previous & concomitant medication & treatments *	X	X	X	X	X	X	X	X
Vital signs (blood pressure, pulse rate)	X	X	X	X	X	X	X	X
12-lead ECG ^a and Auscultation	X							
Body weight	X							X
Body height	X							
Physical and neurological examination	X							X
TETRAS ADL subscale by subject *	X	X	X	X	X	X	X	X
TETRAS Performance subscale by investigator	X ^b	X ^b	X	X ^b	X	X	X	X
TETRAS independent video rating ^c	X							
Kinematic tremor assessment with TremorTek (dominant arm)	X	X	X	X	X	X	X	X
QUEST by subject*		X		X				X
Subject's GICS *				X				
Investigator's GICS				X				

M602011069	Screening	Cycle 1: Double-blind unilateral treatment period						
	Screening visit	Study baseline visit	Control visits					End-of-Cycle 1 visit
Timepoint		Day 1	WEEK 4	WEEK 6	WEEK 8	WEEK 12	WEEK 18	WEEK 24
Study day	-21 to -3	1	28	42	56	84	126	168
Visit window (days)	19		±3	±3	±3	±7	±7	±7
Visit no.	V1	V2	V3	V4	V5	V6	V7	V8
HHD(grip strength) in both hands		X	X	X	X	X		X

AE *	X	X ^d	X	X	X	X	X	X
AESI questioning *		X ^e	X	X	X	X	X	X
Suicidality assessment *	X	X	X	X	X	X	X	X
Global assessment of tolerability								X
Pregnancy test ^f	X	X						X
Coagulation test (INR or aPTT) ^g	X							
Pre-injection coagulation test (INR) ^h		X						
Blood sampling for safety	X							X
Randomization and injections of IP		X						
Eligibility criteria for reinjection ⁱ								X

* If site visits V3-V8 are to be replaced by remote visits (e.g. by phone calls) in case of a public health emergency, e.g. due to a COVID-19 outbreak, assessments with an asterisk should be performed during those visits. Active questioning about possible pregnancy is required for all remote visits (e.g. phone calls).

a. For subjects without a history of any cardiac disease the interpreted copy of an ECG print-out without any clinically significant findings, not more than 3 months prior to the screening visit V1, is acceptable.

b. TETRAS Performance assessment will be video recorded at V1, V2 and V4.

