12.3.5.3 Other safety endpoints

Exposure to study treatment by muscle and treated UL for both study periods.

Incidence of TEAEs, TEAEs of special interest [TEAESIs], serious TEAEs, TEAEs leading to discontinuation, and COVID-19 related TEAEs for both study periods.

Time course (i.e., absolute values and changes from respective baseline) during the unilateral treatment period (Cycle 1) in HHD maximum grip strength (in hand of injected UL) and in maximum grip strength difference between both hands.

Time course (i.e., absolute values and changes from respective baseline) during the bilateral treatment period (Cycle 2) in HHD grip strength in both hands.

[REDACTED]

[REDACTED]

Global assessment of tolerability scale as assessed at Week 24 of unilateral treatment period and at Week 12 of bilateral treatment period.

Time course of vital signs (blood pressure, pulse rate) measurement during both study periods.

Time course of body weight measurement during both study periods.

Time course of standard clinical chemistry and hematology parameter measurements during both study periods.

Time course of suicidality assessment during both study periods.

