- Absolute values of HHD grip strength testing and changes from applicable cycle baseline to all applicable post-baseline visits will be summarized descriptively by treated UL. In addition, for the unilateral phase the intra-individual difference of changes from baseline between body sides will be summarized;

- 

- Time courses of vital signs (blood pressure, pulse rate) and body weight measurement at selected visits and changes from applicable cycle baseline will be summarized descriptively; and
- Time courses of standard clinical chemistry and hematology parameters measurement at selected visits and changes from applicable cycle baseline will be summarized descriptively.

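### Cycle 1 grip strength is summarised by treatment group, but no NT 201 minus placebo difference with a confidence interval and baseline adjustment is specified

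*SAP*

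**What the plan says.** - **Objective.** One secondary objective in Protocol 5 is "Safety of unilateral intramuscular injections of NT 201, as compared with placebo, in subjects with ET of the UL".
- **Background.** On the larger earlier onabotulinumtoxinA trial, Protocol 4.1.2 reports: "Grip strength was reduced for the low- and high-dose botulinum toxin type A groups as compared with the placebo group". It adds: "Hand weakness was found to be a dose-dependent significant side effect of treatment at the doses used in this study". Protocol 8.2.2 gives differing susceptibility of muscles to weakness as one of its reasons for flexible forearm dosing.
- **Data.** The Cycle 1 schedule (Protocol 9.2, Table 5) has "HHD(grip strength) in both hands" at baseline and at Weeks 4, 6, 8, 12 and 24, but not at Week 18.
- **Endpoint tier.** Protocol 12.3.5.3 lists grip among the other safety endpoints: the time course "in HHD maximum grip strength (in hand of injected UL) and in maximum grip strength difference between both hands".
- **Analysis.** Protocol 12.4.5.3 says that grip values and changes "will be summarized descriptively by treated UL". SAP 4.5.3 plans "Descriptive statistics for HHD maximum grip strength [Newton] (values and changes from applicable cycle baseline" and so on by visit. SAP Section 4 defines descriptive statistics for metric variables as n, mean, SD, median, quartiles and range. For Cycle 1 the SAP adds that "the intra-individual difference of changes in maximum grip strength from study baseline between hand of treated and hand of untreated UL will be analyzed".
- **Display.** SAP 4.5 places every Cycle 1 safety analysis on the SES-UP by actual treatment group. Protocol 12.4.5 has the same default.

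**The concern.** The only contrast that the SAP defines for grip is between a subject's two hands. That is not the contrast in the objective, which is NT 201 against placebo. For the between-group question the reader gets two columns of summary statistics per visit and must do the subtraction and judge the uncertainty alone.

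The treatment is also uneven within the SAP. The other secondary efficacy endpoints of the unilateral period (TETRAS ADL Functional Impact and both GICS scores, SAP 4.1.2.2) are also interpreted only descriptively. Yet they receive the full ANCOVA with an LS-mean treatment difference and 95% CI. An instrumental measure of a toxicity that the protocol highlights does not.

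At stake is whether the report can state how large a grip loss, relative to placebo, the data are compatible with.

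**Working it through.** **1. The plan's own figure.** Protocol 12.1 and SAP 5 state 51 analyzable subjects for a 1 SD effect, 5% type I error, 2:1 allocation and 90% power; the tests are two-sided (SAP 4).
- Normal approximation: placebo n = (1 + 1/2) × (1.960 + 1.282)² / 1² = 15.8, so 16 + 32 = 48.
- Noncentral t: power is 0.892 at 16 + 32 and 0.910 at 17 + 34.

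The smallest exact 2:1 total that reaches 90% is therefore 51, and the figure reproduces. It concerns the primary endpoint. The documents give no SD, margin or precision target for grip, so everything below is in units of the SD of the analysed change.

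**2. What the plan yields for grip in Cycle 1.**
- By group and visit: n, mean, SD, median, quartiles and range of the value and of the change in the injected hand.
- By group: the same statistics for change in the injected hand minus change in the non-injected hand.
- Between groups: no difference, interval, test or model.

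**3. Precision of the missing estimate.** SE = SD × √(1/n_placebo + 1/n_NT201); half-width = t × SE. Equal SDs are assumed.

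| NT 201 / placebo | SE | 95% half-width | Power for true 0.5 SD | Difference with 80% power |
|---|---|---|---|---|
| 50 / 25 (Protocol 7.1) | √(0.02 + 0.04) = 0.245 SD | 1.993 × 0.245 = 0.49 SD | 52% | 0.70 SD |
| 34 / 17 (51 analyzable) | √(0.0294 + 0.0588) = 0.297 SD | 2.010 × 0.297 = 0.60 SD | 38% | 0.85 SD |

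Fixed effects for about 15 sites and one covariate leave 75 − 1 − 1 − 14 − 1 = 58 degrees of freedom. Then t is about 2.00 and the half-width stays at 0.49 SD. Baseline adjustment reduces the residual SD by an amount that the documents do not allow one to quantify.

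**4. Whether the adverse event tables fill the gap.** Muscular weakness is an AESI and is tabulated by preferred term and group. Protocol 4.3 reports it in two NT 201 subjects (10.5%, which implies 2/19) in the sponsor's earlier study. At that rate about 5 of 50 would be expected. The placebo counts below are assumptions.
- 5/50 against 0/25: difference 10.0 points, Newcombe 95% CI −4.5 to 21.4.
- 5/50 against 1/25: difference 6.0 points, 95% CI −10.5 to 17.8.

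The AESI incidence is informative, but on its own it gives an imprecise comparison.

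**The case against.** A reader might infer that grip is never compared with placebo and that the safety objective has no estimate for it. The documents do not support that. The by-group rule in SAP 4.5 places NT 201 and placebo next to each other at each visit, and n, mean and SD per group are enough to compute an unadjusted difference and interval. Nor is the reader left with raw group means. The SAP uses change from baseline and, in addition, the injected-minus-non-injected change, which uses each subject's other hand as a control. ANCOVA would improve on this, but its absence does not make the summaries invalid.

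Other points for the sponsor also stand:
- The designated secondary safety endpoint is the incidence of related TEAEs. Grip sits a tier lower, and descriptive safety analysis is common in phase 2.
- Muscular weakness is actively asked about and tabulated.
- The earlier grip findings came from fixed doses of another toxin product, injected only in wrist flexors and extensors. The sponsor's own NT 201 study reported mild finger weakness in two subjects.
- Text next to grip strength is redacted in both documents, so another strength analysis may exist.

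These points limit the concern without removing it. An interval interpreted descriptively is still a descriptive analysis, and the SAP already takes that approach for the non-confirmatory efficacy endpoints. The fact that a reader could derive an unadjusted interval does not make it a prespecified, baseline- and site-adjusted one.

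**Conclusion.** The point holds in a limited form. In Cycle 1, grip strength is summarised by group without a specified NT 201 minus placebo difference, 95% CI or baseline adjustment. The objective of safety against placebo is therefore served, for this measure, only by a crude side-by-side reading. This is a worthwhile improvement to make. It does not invalidate the safety objective.

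The missing interval would have a half-width of about 0.49 SD with 50 versus 25 subjects, or 0.60 SD with 34 versus 17, assuming equal SDs and complete grip data. A reader might take 0.49 SD to mean that a true loss of 0.5 SD would be detected. It would be detected only about half the time (52%). The gain is a bounded estimate. The documents give neither a grip SD nor a threshold for a meaningful loss, so the bound cannot be converted to Newtons or judged clinically here. No conclusion is drawn about redacted strength assessments.

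**What to change.** In SAP 4.5.3, for Cycle 1 on the SES-UP by actual treatment, add the LS-mean difference (NT 201 minus placebo) with 95% CI for:

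- (a) change from study baseline in maximum grip strength of the injected hand;
- (b) the already derived injected-minus-non-injected difference in change.

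Use the ANCOVA of SAP 4.1.1.1 with actual treatment, site and the matching study-baseline value as covariate: injected-hand grip for (a), the injected-minus-non-injected grip difference for (b). Report Weeks 4 and 6 at minimum; Weeks 8, 12 and 24 are optional. State that the intervals are descriptive and use no alpha. If the treatment codes have already been opened, label the analysis post hoc.

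The cost is one table from existing model code, with no change to data collection, sample size or error control. The downside is a set of exploratory intervals without multiplicity adjustment, to be labelled as such: 2 variables × 2 visits = 4 at minimum, or 2 × 5 = 10 if all grip visits are used.

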4.6 Other Analyses

4.6.1 Other Variables

Other variables will be summarized descriptively by treatment group and in total if not stated otherwise.

- Enrollment variables will be analyzed overall and by study site. Absolute and percent frequencies will be displayed for all variables except for “Subjects screened” (absolute frequencies only).
 - “Subjects randomized”, “Subjects treated in Cycle 1”, “Subjects treated in Cycle 2”, Subjects in FAS-UP, Subjects in FAS-BP, and Subjects in PPS will be analyzed on all randomized subjects
 - “Subjects in SES-UP” and “Subjects in SES-BP” will be analyzed based on the SES-UP.
- Variables on study completion/ premature discontinuation of participation will be summarized using frequency tables. Analyses for Cycle 1 and the total observation study will be based on the SES-UP, those for Cycle 2 on the SES-BP.
- Visit attendance variables will be analyzed overall and by treatment group for all visits defined in visit schedules for Cycle 1 and Cycle 2 the CSP (see CSP Tables 5 and 6, respectively). Frequency tables will be created based on all randomized subjects for Cycle 1 and based on SES-BP for Cycle 2.
 - For “Subjects expected at visit”, absolute frequencies will be reported. All randomized subjects are expected for Screening visit (V1) and study baseline (V2). For all following visits in Cycle 1, the number of “Subjects expected at visit” will be the number of randomized subjects not yet having prematurely discontinued study participation until respective visit. Visits after premature discontinuation are generally not expected. The number of “Subjects expected at visit” is thus calculated for all post-study baseline visits in Cycle 1 as number of randomized subjects – the number of randomized subjects that discontinued study participation before the respective visit.
 - For Cycle 2 baseline, the number of subjects expected at visit will be the number of subjects in SES-BP. For all following visits in Cycle 2 [including Week 12 (V11)], the number of “Subjects expected at visit” will be the number of subjects in SES-BP not yet having prematurely discontinued study participation until respective visit. Visits after premature discontinuation are generally not expected. I.e., V11 (Week 12) will only be displayed for subjects in SES-BP.
 - For “Subjects expected at visit”, percentages will be calculated relative to the number of subjects randomized for visits in Cycle 1 and relative to the number of subjects treated in Cycle 2 for visits in Cycle 2.
 - For “Visit performed” and “Visit not performed”, absolute and percent frequencies will be provided. Percentages of columns will be calculated relative to the number of subjects expected at the respective visit.

In case of premature study discontinuation, eCRF question ‘Visit was performed’ will automatically be set to ‘No’ in the eCRF for all visits after premature discontinuation of study participation (except for V11 among subjects in the SES-BP). Therefore, for ‘Visit not performed’ this question will not be used. The number

of subjects with 'Visit not performed' is calculated as number of "Subjects expected at visit" – number of subjects who performed visit.

- For "Study prematurely discontinued", cumulative absolute frequencies will be provided per visit. Absolute frequencies¹⁸ will be determined as numbers of subjects who discontinued study participation before or on the respective visit, but after the preceding visit. For cumulative absolute frequencies, the number of subjects who discontinued the study before or at the respective visit will be displayed.

All performed and all not performed visits until regular study completion or premature study discontinuation (as applicable for the respective subject) will be listed by subject. Flags will also be included for visits performed virtually, visits not performed/ not performed due to COVID-19 pandemic (if applicable).

- Absolute und percent frequencies of subjects excluded from analysis sets will be reported by exclusion reason based on all randomized subjects.
- Demographic data will be summarized descriptively for SES-UP and FAS-UP.

BMI will be calculated as follows:

$$\text{BMI [kg/m}^2\text{]} = \text{weight [kg]} / (\text{height [cm]} * 100)^2 \text{ (rounded to two decimal places)}$$

- Variables on history of ET will be summarized descriptively for SES-UP.

Duration since age of onset of ET [years] will be calculated as age of onset of ET estimated by patient – age as recorded at enrollment, i.e., at Screening (V1)

- Absolute and percent frequencies of previous and concomitant medication will be given on the basis of second and third ATC code levels (Anatomical Therapeutic Chemical classification system of the World Health Organization; WHO Collaborating Centre for Drug Statistics Methodology, ATC classification index with defined daily doses, 2023.) as well as by generic name for the SES-UP. Indications for previous and concomitant medication will not be coded and will only be listed. Separation of previous from concomitant medication is described in [Appendix 8.3](#).
- Medical history, concomitant diseases, previous non-drug treatments (procedures) and concomitant non-drug treatments (procedures) will be coded using the Medical Dictionary for Regulatory Activities (MedDRA, version 26.1) and for SES-UP displayed in frequency tables with respect to SOC and PT. Separation of medical history and concomitant diseases and TEAEs is described in [Appendix 8.4](#). Separation of previous from concomitant non-drug treatments (procedures) is described in [Appendix 8.3](#).
- ECG data will only be listed.
- Injection cycles length and total observation period will be summarized using descriptive statistics for metric variables. Length of Cycle 1 and total observation period will be analyzed based on the SES-UP, length of Cycle 2 based on SES-BP.

The length of an injection cycle and the total observation period will be determined as follows:

The date of injection will be regarded as start of a treatment cycle and the day before the next injection will be regarded as end of cycle. For a discontinued last cycle, the

¹⁸ not to be displayed, only for calculation of cumulative absolute frequencies

maximum of (date of last contact, last visit and last AE start date) will be regarded as end of cycle.

The length of an injection cycle and the total observation period in weeks will be calculated as (end date – start date + 1)/7 (rounded to one decimal), which means:

- The total observation period in weeks over the entire study will be calculated as (maximum of date of last contact, last visit and last AE start date - date of first injection +1 day)/7.
- The injection cycle length of cycle (x) in weeks will be calculated as (Date of injection in cycle (x+1) - date of injection in cycle (x))/7
or (whenever the afore formula cannot be applied) as (Maximum of [date of last contact, last visit and last AE start date] – date of injection of last or discontinued cycle (x) +1 day)/7.
- Injection guidance technique by muscle will be analyzed using frequency tables, including categories “EMG”, “Electrical stimulation”, “Ultrasound” and all combinations which occurred. For calculation of percent frequencies, the number of subjects in the applicable analysis set treated at respective muscle for injection guidance technique at that muscle will be used as denominator (i.e., the sum of absolute frequencies over the first three afore-listed categories). The denominator is defined as number participants in analysis set by treatment group/ in total treated at respective muscle. It will be displayed in the table as “Muscle treated”.
 - For Cycle 1, the analysis will be performed by treatment group on the SES-UP for the treated UL, irrespective of whether the motor dominant UL (acc. to CSP) or the non-dominant UL was treated.
 - For Cycle 2, the analysis will be performed by motor dominant / non-dominant UL on the SES-BP. In case, deviating from CSP, not all subjects in SES-BP were treated at both ULs, the analyses will be performed on the respectively treated subset of subjects only and an explanation (including the following details on affected subjects: Subject ID, treatment group, whether motor dominant non-dominant UL was not treated) will be provided in a footnote.

